#### 16.1.1. Demographics

Demographic data will be summarized with descriptive statistics for gender, age, date of diagnosis of disease, prior treatments and ECOG status (e.g. N, mean, median).

#### **16.1.2.** Concomitant Medications or Treatments

Concomitant medications will be presented in data listings.

#### **16.1.3. Primary Endpoint**

Safety is the primary endpoint. AEs and SAEs will be coded, graded and summarized by attribution. Safety analysis will be performed on all subjects who receive any dose of study medication. AEs that occur after the Safety Evaluation Period will not be included in safety evaluations.

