## **Brief Description of the Protocol:**

This is a single center, open label study comparing CryoVaxTM personalized anti-tumor vaccine protocol combining the cryoablation of a selected metastatic lesion with intra-lesional immunotherapy with AlloStim® alone. The treatment schedules both have the following steps: (1) priming with intradermal AlloStim®; (2) vaccination combining cryoablation with intratumoral AlloStim® or intravenous AlloStim® dosing in the place of cryoablation; (3) activation with intravenous AlloStim®; and (4) booster with intravenous AlloStim®. All subjects are followed for safety during the dosing period and until 28 days following the last dose (Safety Evaluation Period"). All subjects are continued to be followed for survival after the Safety Evaluation Period.

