### Dosing Schedule A-1: Intradermal and Intravenous Dosing Combined With Cryoablation

The priming step: Subjects will receive an ID injection of AlloStim® (0.5ml) on Days 0, 7, and 14 all in different locations.

The vaccination step: Subjects will receive cryoablation and intratumor (IT) injection of AlloStim® (3 ml) on Day 21.

The activation step: Subjects will receive an IV infusion of AlloStim® (3ml) on Day 28. The booster step: Subjects will receive two (optional) IV booster infusions of AlloStim® (5ml), one on Day 56 and Day 84.

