# **14.6.** CONCOMITANT TREATMENTS PROHIBITED AND RESTRICTED THERAPIES DURING THE STUDY

No chemotherapy or other anti-cancer treatment is allowed within the first 140 days for Schedules A1-4 subjects and 105 days for Schedule B, C, D, E and F subjects ("Study Period"). If the PI determines that a subject requires anti-cancer treatment during the Study Period, the subject data will be dropped from the protocol. The safety data will be reported but will be censored as of the treatment date. An additional subject will be accrued for each censored subject.

Subjects with bone metastases may receive palliative radiation therapy to treat pain or prevent pathological fractures during the Study Period.

Subjects experiencing anemia can be transfused as medically required (e.g., if Hgb < 9.0) at discretion of the PI. Erythropoietin may be used in continuation therapy, if indicated.

Subjects will receive medically appropriate supportive care, including treatment of pain and infection during the Study Period.

Additional IV booster infusions are allowed at the discretion of the investigator on a monthly basis after the completion of the Study Period.

Use of steroids is not allowed unless medically indicated. NSAIDs should be used as first choice and methylprednisone or SoluMedrol as next choice if anti-inflammatory medication

is deemed necessary. Inhaled steroids are allowed on study. If a subject is administered systemic steroids during the Study Period for any reason, the subject will be dropped from the study and the data will be censored from the first day of steroid administration.

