#### **15.3.** Adverse Events Reporting

#### 15.3.1. Reporting Requirements

- The adverse events reporting period for this trial begins upon receiving the first dose of investigational product and ends on the last day of the Safety Evaluation Period.
- All adverse events that occur in trial subjects during the adverse events reporting period specified in the protocol must be reported to the Sponsor, whether or not the event is considered study medication related.
- In addition, any known untoward event that occurs subsequent to the adverse events reporting period that the investigator assesses as possibly related to the study medication should also be reported as an AE.
- The investigator also should comply with the IRB/IEC procedures for reporting any other safety information.
- All AEs should be reported to the Sponsor within 10 calendar days.
- All SAEs must be reported to Sponsor immediately (within 24 hours) upon knowledge.
- The Sponsor shall forward these AE reports to the Data Safety Monitoring Board.
- The Sponsor shall forward all SAE reports to the Data Safety Monitoring Board immediately upon receipt.

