#### **15.7.** STOPPING RULES

An external DSMB will oversee this study. The investigators and representatives of the Sponsor and DSMB will review and discuss subject data for all subjects enrolled by teleconference. The DSMB could recommend stopping the clinical trial for safety purposes.

The development of dose limiting toxicity (DLT) in any subject will prompt a review of safety data by DSMB. The development of any DLT toxicity in  $\geq 33\%$  of the accumulated number of subjects at any dosing during the assessment period (28 days after last booster infusion) will result in protocol discontinuation. However, if DTLs only occur in the Activation or Booster phase, then a decision by DSMB may be made to continue enrolling subjects to receive only priming and in-situ vaccination phases.

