#### 16.1.4. Adverse Events

All reported terms (investigator descriptions) for AEs will be coded using the Medical Dictionary for Regulatory Activities (MedDRA). The incidence of AEs will be summarized for those events that occur on or after the date of the first treatment (TEAE: Treatment-Emergent Adverse Events). All SAEs and TEAEs leading to withdrawal, and or other significant TEAEs will be listed separately. The data will be summarized as follow:

- all TEAEs,
- TEAEs related to Study drug,
- Serious TEAEs,
- Serious TEAEs related to Study drug,
- TEAEs resulting in death,
- TEAEs leading to withdrawal.

The incidence of TEAEs will be summarized by system organ classification and preferred term by severity and relationship to study medication. All AEs will be included in the data listings.

Laboratory results will be classified according to NCI-CTCAE Version 4.03. Incidence of laboratory abnormalities will be summarized; laboratory results not corresponding to an NCI-CTCAE Version 4.03 term will not be graded. Laboratory toxicity shifts from baseline to worst grade will also be provided.

The results from medical history, physical examination, and vital signs measurements will be tabulated.

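### Section 16.1.3 leaves late drug-related AEs out of the primary safety summaries, conflicts with the open-ended TEAE definition in 16.1.4, and relies on a period whose end is undefined when extra boosters are given

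*Combined protocol and SAP*

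**What the plan says.** Section 16.1.3 names safety as the primary endpoint, analysed in everyone who received any study medication, and then limits it in time: "AEs that occur after the Safety Evaluation Period will not be included in safety evaluations".

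Other parts of the plan bear on the same window:

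- **Length of the period.** The abstract's brief description has subjects "followed for safety during the dosing period and until 28 days following the last dose". Section 15.7 describes its assessment period as "28 days after last booster infusion".
- **Reporting.** Section 15.3.1 ends routine AE reporting on the last day of the Safety Evaluation Period, but it also says that sites should report "any known untoward event that occurs subsequent to the adverse events reporting period that the investigator assesses as possibly related to the study medication". Section 15.1.3 has subjects asked about AEs by telephone at least monthly in follow-up. Section 15.2 sets a post-study SAE window of 30 days after the last IV booster.
- **Analysis.** Section 16.1.4 summarises AEs for "those events that occur on or after the date of the first treatment", with no end date, and puts all AEs in the data listings.
- **Extra dosing.** Section 14.6 states: "Additional IV booster infusions are allowed at the discretion of the investigator on a monthly basis after the completion of the Study Period". For the A schedules the Study Period is 140 days. No maximum number of extra boosters is given.

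**The concern.** The protocol asks for late related toxicity to be reported and then leaves it out of the evaluation of its primary endpoint. The rule has no carve-out for causality, so an event that the investigator attributes to AlloStim is treated like an unrelated one if it starts after the period closes.

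Sections 16.1.3 and 16.1.4 also give different tables. Under 16.1.4 a late AE is a TEAE and enters the incidence summaries; under 16.1.3 it does not. Two programmers following the same plan could produce different primary safety results.

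This matters for this product. Section 6.8.1 describes an intended cytokine storm and a sustained inflammatory state, and Section 15.1.2 asks for particular vigilance for immune-related events. Section 7.1 makes it a primary objective to find the schedule with the best balance of efficacy and adverse events. With about 6 subjects in Part 1, a single omitted related event could change how a schedule looks.

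**Working it through.** The plan states no AE rate, power or precision figure for this endpoint, so there is no figure of its own to reproduce. The check is date arithmetic, a comparison of the rules, and an illustration under assumed rates.

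**1. When the period closes if only scheduled boosters count.** Section 8 places the A-1 boosters "one on Day 56 and Day 84" and the last A-2 booster on Day 77.

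- A-1: 84 + 28 = Day 112
- A-2: 77 + 28 = Day 105

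**2. Where the extra boosters fall.** They come after the 140-day Study Period, so on Day 141 at the earliest.

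- A-1: 141 − 112 = 29 days after the period has closed
- A-2: 141 − 105 = 36 days after

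On this reading, AEs after an extra booster are outside the evaluated window.

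**3. When the period closes if every dose counts.** An extra booster on Day *d* moves the end to *d* + 28. AEs up to that day are included, and only later ones are left out.

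**4. Which reading applies.** The text does not say. The abstract's reference to the last dose and Section 15.7's reference to the last booster both allow the second reading. Two features fit the first better: Section 8 closes the Part 1 safety evaluation when the period is complete for all cohorts, and the abstract schedules weekly laboratory tests throughout the period. Both are awkward with open-ended monthly dosing, but neither settles it.

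**5. What holds under both readings.** A related AE that starts more than 28 days after the last dose is reportable under 15.3.1, a TEAE under 16.1.4, and excluded under 16.1.3. A related SAE on days 29 to 30 after the last IV booster is inside the Section 15.2 window but outside the 28-day period.

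**6. Illustration of size.** Let *p* be the assumed share of subjects with a related AE after the period. Subjects left out on average = *np*; chance of at least one = 1 − (1 − *p*)^*n*. Section 10.1 gives *n* = 6 for Part 1 and 6 + 25 = 31 as the maximum overall. The values of *p* are assumptions.

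| *p* | *n* = 6: at least one | *n* = 31: average left out | *n* = 31: at least one |
|---|---|---|---|
| 2% | 11% | 0.6 | 47% |
| 5% | 26% | 1.6 | 80% |
| 10% | 47% | 3.1 | 96% |
| 20% | 74% | 6.2 | 99.9% |

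For example, at 5% and *n* = 31: 1 − 0.95^31 = 0.80.

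**The case against.** The strongest case against is that little is actually lost. Section 16.1.4 keeps all AEs in the listings and lists SAEs separately. Section 15.3.1 sends AE reports to the DSMB, and Section 15.2.2 requires SAE reporting through the last follow-up visit. The analysis is descriptive, and the sentence in 16.1.3 does not govern the stopping rules in Sections 8 and 15.7. All of this stands. It limits the defect to the summaries and argues against treating it as critical, but listings do not replace a summary of the primary endpoint.

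A bounded window also has a rationale. Section 6.2 allows regorafenib or TAS-102 after the Safety Evaluation Period, and the Section 15 causality table lets an event count as possibly related when another cause is equally likely. Putting late events into the main tables would mix in toxicity of salvage therapy and unequal follow-up. This also stands, and it is why the fix below uses a separate table.

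A reader might infer that the plan discards every AE after an extra booster. The documents do not support that: it is true only if the period is anchored to the scheduled boosters, which no section states. Nor do they support saying that late AEs are lost altogether, or that reporting possibly related late events is mandatory; Section 15.3.1 says they should be reported.

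**Conclusion.** The concern holds in a limited form. Section 16.1.3 excludes late related AEs from the primary safety summaries and conflicts with 16.1.4. The direction is certain if 16.1.3 is followed: related toxicity can be under-counted and cannot be over-counted. The size cannot be determined from the documents, and the table above rests entirely on assumed late-event rates.

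Separately, the end of the Safety Evaluation Period is not defined for subjects given extra boosters. That is an ambiguity, not proof that events after those boosters are excluded. No estimate based on a count of infusions left uncounted is justified, because it would need the scheduled-booster reading, a number of extra boosters and a risk per infusion, none of which the documents give.

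This should be fixed. It is not critical, because the data remain in the listings and the correction is mostly wording.

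**What to change.** 1. Replace the sentence in 16.1.3. AEs and SAEs after the Safety Evaluation Period that are assessed as possibly, probably or definitely related should be summarised by schedule in a separate post-period table within the primary safety report, with events that start after salvage anti-cancer therapy flagged.
2. For analysis, define the end of the period as 28 days after the last AlloStim dose actually given, extra boosters included, and show the scheduled-dosing period separately. Align the AE reporting period in 15.3.1 with this.
3. Use the same window for TEAEs in 16.1.4, and reconcile the 28-day window (abstract, Section 15.7) with the 30-day SAE window (Section 15.2).

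**Cost.** One or two extra tables and slightly higher reported AE rates. Possibly related late events are already reportable, so the post-period table needs little new data. Counting all AEs after extra boosters does need some added recording: if those boosters now lie outside the period, 15.3.1 does not ask for unrelated events then, and Tables 1 and 2 schedule no assessment after Day 91.

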#### 16.1.4. Adverse Events

All reported terms (investigator descriptions) for AEs will be coded using the Medical Dictionary for Regulatory Activities (MedDRA). The incidence of AEs will be summarized for those events that occur on or after the date of the first treatment (TEAE: Treatment-Emergent Adverse Events). All SAEs and TEAEs leading to withdrawal, and or other significant TEAEs will be listed separately. The data will be summarized as follow:

- all TEAEs,
- TEAEs related to Study drug,
- Serious TEAEs,
- Serious TEAEs related to Study drug,
- TEAEs resulting in death,
- TEAEs leading to withdrawal.

The incidence of TEAEs will be summarized by system organ classification and preferred term by severity and relationship to study medication. All AEs will be included in the data listings.

Laboratory results will be classified according to NCI-CTCAE Version 4.03. Incidence of laboratory abnormalities will be summarized; laboratory results not corresponding to an NCI-CTCAE Version 4.03 term will not be graded. Laboratory toxicity shifts from baseline to worst grade will also be provided.

The results from medical history, physical examination, and vital signs measurements will be tabulated.

#### 16.1.5. Secondary Endpoint (Part 2 only)

Health-Related Quality of Life will be measured at baseline, during the treatment (for subjects enrolled to schedules A1-4 at day 35 and for subjects in schedules B-F at day 28) and after completion of treatment (28 days following the last booster dose). Analysis will be performed to compare quality of life differences over the time.

#### **16.1.6. Exploratory Endpoints**

All data will be summarized using descriptive statistics by dosing schedule. All subjects who received any study medication will be included in the analysis.

If the subject is alive at the end of the follow-up period or is lost to follow-up, OS will be censored on the last date the subject is known to be alive.

#### 16.1.7. Missing and Spurious Data

Every effort will be made to obtain required data at each scheduled evaluation from all subjects who have been enrolled. There will be no imputation for missing data.

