#### **Radiology Assessment:**

All subjects will undergo a CT scan of the head, chest, abdomen and pelvis with and without contrast (contrast can be withheld if medically indicated) at baseline and at Day 91 at same time as biopsy.

As it is difficult to determine if subjects are responding or progressing after immunotherapy by standard radiological methods and RECIST criteria, the analysis of the CT scans is conducted as an experimental end-point. It is known that after immunotherapy that subjects can develop new lesions, experience lymphadenopathy and interval size increases in tumors. These changes would normally be documented as progression. However, in immunotherapy, the changes could represent "pseudo-progression". In some cases, the changes could indicate actual progression, but a response can still occur months after immunotherapy. Other times, immunotherapy can cause a stable disease condition that results in increased survival.

The changes in the images will be analyzed by RECIST and other accepted and novel experimental methods in order to retrospectively determine a method that best correlates with survival outcomes. The CT scans are scheduled on the same day as biopsy procedures in order to correlate the radiological images with pathological response. It is believed that patterns of necrosis, fibrosis and immune cell infiltration patterns with HU numbers on the radiographic images may provide correlates that could distinguish immune response from progression or be predictive of a survival response. Radiographic images can be reviewed by the site radiologists according to established methods. At the discretion of the PI, select subjects may be further evaluated by MRI or PET in order to attempt to distinguish between radiological "pseudo-progression" due to an immune response and actual progression.

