In accordance with the 3+3 design, three subjects will be accrued into the first dosing schedule. If during the priming, vaccination and activation steps no ADLT are observed in any of the three subjects, accrual into the next cohort is allowed. If an ADLT occurs in two of the three subjects, no further dosing is allowed. If ADLT occurs in one of the three subjects, three additional subjects will be accrued into the same cohort. If no ADLT occurs within the additional three subjects, accrual into the next cohort can begin. If an ADLT is observed in any of the additional three subjects, no further dose escalation is permitted.

The development of any DLT toxicity in  $\geq$  33% of the accumulated number of subjects in any and all dosing schedules during the Safety Evaluation Period will result in protocol discontinuation.

At the completion of the Safety Evaluation Period for all cohorts, the safety evaluation of Part 1 will be considered completed and all enrollment will be closed. Efficacy evaluation will continue monthly for each subject until death or loss to follow-up.

# Part 2

The safety and efficacy data from Part 1 will be evaluated and the favored schedule advanced to Part 2. In Part 2 of the trial, up to 25 additional subjects may be accrued.

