# **9.2. EXPLORATORY ENDPOINT**

- Correlation of tumor burden by RECIST, pathological response and immune response to Overall Survival (OS).
  - Overall Survival (OS) is evaluated from time of enrollment until death from any cause. Subjects are followed for survival during the trial, as long as they are alive, for 12 months after the last study treatment through follow-up phone calls.
  - Traditionally, oncology investigators have relied upon Response Evaluation Criteria in Solid Tumors (RECIST) to serve as a surrogate to predict clinical benefit. RECIST criteria for clinical outcomes rely upon the assumption that agent activity results in shrinkage of tumor and that enlargement of disease is a result of tumor growth. RECIST is a composite evaluation of response based upon measurements of the changes in tumor size [82]. RECIST criteria have been criticized for not being a reliable method to predict OS benefit for cytotoxic agents [83].

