# **11.2.** Study Procedures

#### **11.2.1.** Physical Examination

A Comprehensive Physical Examination will be conducted at baseline. The exam will include the following organ systems: Constitutional; Eyes; Ears, Nose, Mouth and Throat; Neck; Respiratory; Cardiovascular; Gastrointestinal (abdomen); Lymphatic; Musculoskeletal; Skin; Neurologic; and Psychiatric. Subjects should be carefully screened at baseline for depression and suicide attempts or ideations. If there are indications or a history of depression is strongly recommended that these patients be closely followed together with behavioral health or psychiatric medical support. Subjects with an established diagnosis of depression or reported previous suicide attempts or suicidal ideations should not be enrolled on this protocol; the risks and benefits of being treated with the study drug should be weighed very carefully in consultation with behavioral health or psychiatry.

A Basic Physical Examination will be performed at each subject visit, the presence of lymphadenopathy, edema, rash or pain will be recorded. The subject's psychological status will be evaluated as part of the physical examination in each study visit. Information on exam will be documented in the medical record and on CRF/eCRF.

Subjects will be evaluated for response by laboratory blood tests, radiological, pathological and immunological tests, as well as by performance status in order to determine if there is evidence of disease progression. Subjects that have clinically deteriorated and do not show evidence of response, in the judgment of the PI, will be discontinued on further experimental treatment and advised of alternative treatment options.

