#### 11.2.4. Tumor Assessment

CT scan of the Head/Chest/Abdomen/Pelvis with and without contrast (if tolerated) will be conducted at baseline and Day 91. All subjects accrued in schedule A-1 will also be evaluated at baseline to confirm they have a liver lesion that can be readily visualized and safely approached percutaneously for cryoablation.

Subjects will undergo mandatory tumor biopsies of at least one selected target lesion (not lesion targeted for ablation) at baseline, during intratumoral injections (day 21 Schedule A1 and on Day 91.

The intratumoral procedures use a trocar that will have already been inserted into the tumor to conduct the intratumoral injection and thus these biopsies will not add an additional invasional procedure.

In order to obtain information on the longitudinal changes in the immune cell patterns of tumors as well changes in tumor size, biopsies will be collected for subjects who consented under a separate inform consent. These additional biopsies will be conducted only if subjects separately consent. Failure to consent for the intermediary biopsy procedures will not disqualify subjects.

The biopsies material should be placed in containers supplied by the Sponsor. The samples should be labeled with protocol number, subject study ID, date of birth, date of sample collection and sample time point (protocol day). The containers should be kept at room temperature (RT) and delivered to Sponsor's histology lab within 24h of collection to:

> [name], MD (Pathologist): Immunovative Clinical Research, Inc., [name]

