# **12.1.** SCHEDULE DEVIATIONS

Scheduled protocol activities should be conducted on the specified protocol days. In some cases the scheduling may not be able to be followed precisely. For example, subjects may miss appointments causing deviations due to illness, weather, transportation problems or miscommunication. The clinic may experience deviations in scheduling due to lack of available site personnel, lack of available supplies, mechanical or equipment failures. Deviations may also occur due to unavailability of the study drug, due to QC failures or study drug transport problems. In addition, holidays and weekend scheduling may cause conflicts.

If a scheduled protocol appointment is missed for any reason and the study drug has already been shipped, the protocol procedure can be delayed by one or two days, as long as the study drug is delivered within its 72 hours shelf life time. If the study drug cannot be delivered within the 72 hours shelf-life window, then the protocol procedure should be rescheduled for the next available protocol activity day. When rescheduling protocol treatments, the study drug should not be administered within 3 days of a previous study drug administration. Thus, up to a 7 day delay in protocol procedures is allowed for a missed appoint.

For schedule C, the second intratumoral injection after cryoablation (day 17) must occur 3 days +/- 1 day after the ablation procedure.

Schedules for laboratory and research blood tests and follow-up assessments can deviate +/- 3 days from the scheduled protocol days. Schedules for CT scans can deviate +/- 1 week from the protocol days. All protocol deviations should be documented with the reason and the rescheduling clearly stated on a form provided by the Sponsor for this purpose.

If protocol deviations in treatment days occur more than once or occur outside of the allowed deviation windows, the subject will be censored as of the date of the violating deviation for survival analysis.

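### The plan does not say how a dosed subject with no Day 91 CT counts in the tumor response summary, so that summary can rest on scanned survivors only and read too high.

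*Combined protocol and SAP*

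**What the plan says.** Section 11.2.4 states that CT "will be conducted at baseline and Day 91". Section 12.1 adds a window: "Schedules for CT scans can deviate +/- 1 week from the protocol days". The synopsis (Radiology Assessment) gives the same two time points and adds that, at the investigator's discretion, "select subjects may be further evaluated by MRI or PET". No CT is scheduled at discontinuation; Section 13.2 asks only for an unspecified follow-up evaluation about 28 days after the last dose.

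Three rules bear on a dosed subject who has no Day 91 scan:

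- Section 16.1.6 (exploratory endpoints, summarized descriptively by schedule): "All subjects who received any study medication will be included in the analysis".
- Section 16.1.7: "There will be no imputation for missing data".
- Section 14.6: if the investigator decides that a subject needs other anti-cancer treatment in the Study Period (140 days for the A schedules), that subject's data are dropped, safety data are reported but censored at the treatment date, and an additional subject is accrued.

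Section 11.2.1 describes how some subjects reach that point: "Subjects that have clinically deteriorated and do not show evidence of response, in the judgment of the PI, will be discontinued" from further experimental treatment and advised of alternatives. No section gives such a subject a response category or names the denominator for response.

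The result has a use. Section 7.1 makes finding the schedule with the best efficacy and fewest adverse events a primary objective, and Section 8 (Part 2) says "The safety and efficacy data from Part 1 will be evaluated and the favored schedule advanced to Part 2". No selection rule is given. For survival, Section 9.2 says "Overall Survival (OS) is evaluated from time of enrollment until death from any cause".

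**The concern.** Here a missing Day 91 scan is often a result of treatment failure: the subject has died, has become too ill, or has moved to another therapy. Sections 16.1.7 and 14.6, read literally, leave that subject without a response value. A statistician following them could reasonably divide responders by subjects scanned. That ratio rises as early failures are removed from its denominator, and it rises more in the schedule that has more of them.

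Two uses are exposed: any response or disease control proportion reported for the subjects in Part 2 (up to 25), and the efficacy evidence from three subjects per schedule that helps decide which schedule those subjects receive.

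**Working it through.** The plan gives no response rate, dropout rate or power calculation for this endpoint, so it has no figure to reproduce. Section 16.1.8 justifies at least three subjects per schedule on safety grounds only.

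**Deaths before Day 91.** The inputs are median survival times from the protocol's background: 5.0 and 6.4 months (Section 6.2.7, regorafenib phase III trial); 5.3 and 7.1 months, and 4.9 months for KRAS-mutant placebo patients (TAS-102 section, phase III trial). Survival is assumed exponential. Day 91 is 91/30.44 = 2.99 months, and the share dead by then is q = 1 − 2^(−2.99/median).

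| Median (months) | q | 1/(1−q) | Chance that at least 1 of 3 dies: 1−(1−q)³ |
|---|---|---|---|
| 4.9 | 34.5% | 1.53 | 72% |
| 5.0 | 33.9% | 1.51 | 71% |
| 5.3 | 32.4% | 1.48 | 69% |
| 6.4 | 27.7% | 1.38 | 62% |
| 7.1 | 25.3% | 1.34 | 58% |

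The third column is the factor by which a scanned-only rate exceeds the all-dosed rate if every survivor is scanned. Deterioration and change of therapy would add to the unscanned.

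**Sensitivity.** The TAS-102 section also cites 12-month survival of 27% and 18%. Taking these as whole-trial figures, the exponential model gives 2^(−12/7.1) = 31% and 2^(−12/5.3) = 21%, so it may overstate early deaths somewhat. A Weibull curve S(t) = exp[−ln2·(t/median)^k] through each median and 12-month value has k = 1.21 and 1.11, and gives 22% and 31% dead by Day 91 instead of 25% and 32%. If early mortality were half the exponential range (12.7% to 17.2%), at least one of three would still die before the scan with probability 33% to 43%.

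**Part 2, with 25 dosed and 5 responders.** All dosed: 5/25 = 20%. Scanned at q = 25%: 25 × 0.75 ≈ 19, so 5/19 = 26%. Scanned at q = 34%: 25 × 0.66 ≈ 16, so 5/16 = 31%.

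**Part 1, a reversal.** Schedule X has 2 early deaths and 1 subject with disease control: 1/1 = 100% of scanned, 1/3 = 33% of dosed. Schedule Y has no early deaths and 2 controlled: 2/3 = 67% either way. X leads on scanned subjects, Y on dosed subjects.

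**How often.** Two schedules of three were enumerated exactly, with early-death rates of 25% and 34% and 44% disease control among those scanned in both (44% is the TAS-102 figure, used for illustration only). The two denominators give different rankings, ties included, in 18.5% of trials and fully opposite rankings in 2.0%. In 10.2%, the schedule with the higher early-death rate has more early deaths, no more controlled subjects, and still the higher scanned-only rate. In a further 5.4%, at least one schedule has nobody scanned.

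**The case against.** The strongest reply is that the plan does not exclude these subjects. Section 16.1.6 includes everyone dosed, and declining to impute does not by itself remove anyone from a denominator. That stands: a reader might infer that early failures are removed from the efficacy summary, and the documents do not say so. But inclusion assigns no response category to an unscanned subject, Section 16.1.7 can be cited against scoring one as a non-responder, and Section 14.6 drops some of them outright.

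Second, no response rate is formally defined. The exploratory endpoint is the correlation of RECIST, pathology and immune response with survival, and Sections 9.2 and 11.2.4 caution against relying on RECIST. This lowers the stakes. Descriptive summaries by schedule are nevertheless planned, and Part 1 efficacy feeds the schedule choice.

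Third, early deaths are visible elsewhere. They are events in overall survival, on-treatment deaths in the Safety Evaluation Period are reported as SAEs, and the DSMB reviews deaths. With six subjects they would be hard to overlook. This is a real safeguard for the schedule choice, but it does not correct a response proportion. Survival is also only a partial backstop, because Sections 12.1, 14.6 and 16.1 censor or drop subjects for schedule deviations, other therapy or steroids.

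Fourth, stopping treatment for deterioration does not cancel the Day 91 CT, and Section 16.1.7 promises every effort to collect scheduled data. Some of these subjects will be scanned. Biopsies before Day 91 and discretionary MRI or PET also exist, so it would be wrong to infer that tumor status can be observed only at Day 91; that holds for scheduled CT.

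Fifth, RECIST 1.1 and irRC are adopted by citation and may contain rules for unevaluable subjects. The plan states none, and any such rule would have to be squared with Sections 14.6 and 16.1.7.

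**Conclusion.** The concern holds as an unresolved conflict among Sections 14.6, 16.1.6 and 16.1.7 for tumor response. One permissible reading gives a scanned-only summary that is biased upward by a factor of about 1.34 to 1.53 from early deaths alone. This rests on exponential survival, on medians from other trials, and on every survivor being scanned. ECOG 0-1 subjects may do better early, which would shrink the factor; deterioration and change of therapy would enlarge it.

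The stronger inference, that the plan will tend to pick the schedule with more early failures, is not supported. Full reversals occur in about 2% of the modeled trials, and at three subjects per schedule chance dominates whichever denominator is used. The upward bias in a Part 2 proportion does not depend on any ranking. Tumor response is exploratory and safety is the primary endpoint, so this is a correction that should be made rather than a threat to the trial's main conclusion.

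**What to change.** In Sections 16.1.6 and 16.1.7, state that for descriptive RECIST and irRC response summaries, and for the Part 1 schedule choice:

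- the denominator is all dosed subjects;
- death, clinical deterioration or new anti-cancer therapy before the Day 91 CT counts as non-response;
- a scan missing for any other reason is shown as not evaluable and stays in the denominator, with counts by schedule;
- the scanned-only result is supportive.

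Amend the analysis wording in Section 14.6 so that a subject who starts other anti-cancer treatment stays in this denominator even if an additional subject is accrued.

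Do not carry the assigned non-responses into the correlation of response with overall survival. Coding early deaths as non-response would build that correlation in. Run that analysis among subjects alive and scanned at Day 91.

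The cost is a few sentences of analysis text, with no change to treatment or visits. The drawback for the sponsor is a less favorable reported response rate.
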